1.4 Clinical Studies

In order to further examine if topical application of antimicrobial CoNS can decrease *S. aureus* survival on the skin of AD subjects, we conducted a preliminary double-blind, placebo-controlled autologous microbiome transplant study (AMT) under IND# 15786. An antimicrobial CoNS strain was isolated from the non-lesional

skin of each of 5 AD subjects who were *S. aureus* culture positive. To transiently increase their abundance on each subject, the active strains were expanded and then reapplied to the lesional forearm skin of the same subject, from which the active colonies were isolated, to a final concentration of 1×10^5 CFU/cm², a density similar to previous assessments of the abundance of bacteria on normal human skin. A single application of this functionally defined and autologously-derived CoNS strain(s) decreased *S. aureus* CFU within 24 hours; whereas, vehicle applied to the contralateral arm in a double-blind comparison did not (Fig. 4a-b). However, CoNS survival on the arm 24 hours after AMT was similar to the baseline. These results suggest that a single application of CoNS at a dose of 1×10^5 CFU/cm² was sufficient to transiently decrease survival of *S. aureus*, but the majority of transplanted CoNS died within 24 hours. Therefore, we propose to apply the AMT cream for multiple applications (BID for seven days) for better survival of transplanted CoNS.

[figure not shown]

Figure 4. Transplantation of antimicrobial CoNS reduces survival of *S. aureus* colonized on the skin surface.

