5.1. Risks of Investigational Product

Risk of applying microbial cream (Cetaphil® containing Staphylococcal bacteria)

Skin infection

The likelihood of subjects developing a skin infection is low given that we will be transplanting their non-pathogenic autologous bacteria that have antimicrobial peptide-producing abilities. Since we are transplanting the subject's own endogenous bacteria back onto them, we know that these bacteria are present on the subject's skin at baseline without causing an infection. In addition, the bacteria strains to be transplanted onto the patient will be screened prior to putting it into the AMT cream to ensure that it is not a skin pathogen. The known pathogen *S. aureus* that frequently colonizes AD skin will not even be considered as a potential bacteria to transplant because of its yellow color on mannitol-salt-agar plates, which isolated bacteria will be grown on. Only red colonies (*S. epidermidis*) growing on mannitol-salt-agar plates will be chosen and screened as potential bacteria to be transplanted onto the subject. If anything, we expect the population of *S. aureus* to be reduced with the use of the AMT cream, since the AMT cream will contain only bacteria that are known to inhibit *S. aureus*. Furthermore, we will be applying these bacteria topically and will exam all patients first to ensure that they do not have any cracks or excoriated skin on their arms before we apply it. We will also avoid applying the microbial cream to the hand since the hand would be a likely source of spreading these bacteria onto other surfaces that other people may contact. Should an infection occur (or should the subject be concerned about an infection), the subject should call [name] or [name]. The subject would be treated according to the standard treatment after examination by Drs. [name] or [name]. The treatment will include topical and/or oral antibiotics

(for infection) depending on the severity of the infection clinically, and Cetaphil® moisturizing lotion (for irritation and dryness), provided by Drs. [name] or [name]. The topical antibiotic of choice will be mupirocin. The oral antibiotic of choice will depend on the individual subject's medical history, including any possible contra-indications to certain medications due to allergies or other concomitant medication use, but doxycycline will be the first line oral antibiotic, followed by a cephalosporin or penicillinase-resistant penicillin.

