Visit 5 (Day 7 +/- 7): Subjects will be asked to return to the clinic for Visit 5 approximately 4 hours after last cream application. Subject diaries will be collected at this time. Any used and unused aliquots of cream will be collected at this visit. Subjects will be asked to refrain from bathing, exercising, or showering starting at 12:01am of Visit 5. Vital signs will be taken. Any adverse events since the last visit will be recorded. A brief exam of the skin on subjects' arms will be performed. The severity of AD on each arm will be graded using the localized SCORAD, modified EASI and global SCORAD and EASI grading. Subjects will also be asked to grade their pruritus on a scale of 1-10, with 10 being the worst pruritus of their life. Digital photographs of the lesional skin on both arms will be taken. Next, one culture swab and one to two DNA swabs will be taken from the eczematous skin from each arm, and one culture swab and one to two DNA swabs will be taken from the non-lesional skin on each upper inner arm for a total of up to twelve (12) swabs to determine the microbial diversity and abundance. We expect this visit to take approximately 15 minutes.

Visit 6 (Day 8 +/- 7): Subjects will be asked to return to the clinic for follow-up. Any adverse events since the last visit will be recorded. A brief exam of the skin on subjects' arms will be performed. Subjects will be asked to refrain from bathing, exercising, or showering starting at 12:01am of Visit 6. Vital signs will be taken. The severity of AD on each arm will be graded using the localized SCORAD, modified EASI, and global SCORAD and EASI grading. Subjects will also be asked to grade their pruritus on a scale of 1-10, with 10 being the worst pruritus of their life. Digital photographs of the lesional skin on both arms will be taken. Next, one culture swab and one to two DNA swabs will be taken from the eczematous skin from each arm, and one culture swab and one to two DNA swabs will be taken from the non-lesional skin on each upper inner arm for a total of up to twelve (12) swabs. Any used cream will be collected. We expect this visit to take approximately 15 minutes.

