9.1 Skin swabs Samples

9.1.1. Skin Swab collection

The antecubital fossae bilaterally will be defined as the lesional swab location. The non-lesional swab location will be defined as the upper inner arm without AD skin. The designated site for swabbing will be marked with a pen and non-identifying digital photographs will be taken of the swabbing site for future visits. The designated site for swabbing will be measured for each subject, and the total area (cm x cm) recorded. Using a skin swab, the lateral edge of the swab will be rubbed across the measured area in a cross-wise manner while rotating the swab handle between the thumb and forefinger. Swabbing will be performed for at least 30 seconds. Up to 6 swabs may be obtained from each site.

9.1.2. *Staphylococcus aureus* Screening assay

Skin swabs will be collected from pre-measured areas of lesional and non-lesional skin per Section 9.1.1. Swabs will be resuspended in 1.5 mL tryptic soy broth (TSB) containing 15% (v/v) glycerol. Dilutions of culture medium will then be used to inoculate on mannitol salt agar plates with egg yolk for selective growth of *Staphylococcus* species and differentiation of coagulase-positive and coagulase-negative strains. Plates will be incubated for 24 hours in a 5% CO₂ incubator at 37° C. The plates will be evaluated for the presence of *S. aureus* colonies, which appear yellow with a surrounding clear zone.

9.1.3. 9.1.2. CFU Quantification of Live *Staphylococcus aureus*

Skin swabs will be collected from pre-measured areas of lesional and non-lesional skin per Section 9.1.1. Swabs will be suspended in 1.5 mL tryptic soy broth (TSB) containing 15% (v/v) glycerol and stored frozen at -80°C. Live CFUs of coagulase positive *S. aureus* will be determined by inoculation on a bacterial culture plate containing mannitol salt agar with egg yolk for selective growth of *Staphylococcus* spp. *S. aureus* will be conventionally distinguished from coagulase negative *Staphylococcus* according to mannitol metabolism and the egg yolk reaction, and coagulase positive and negative *Staphylococcus* will be quantified by manual counting of limiting dilutions of the stock solution.

9.1.4. Quantification of *Staphylococcus aureus*, *S. hominis*, *S. epidermidis*, and total *Staphylococcus* DNA by q PCR

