13.2 Endpoints/Outcomes

13.2.1 Primary Endpoint(s)/Outcome(s)

- The change in *S. aureus* abundance after 7 days of AMT cream by using skin swabs to determine the quantity of *S. aureus* using culture and qPCR.

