13.4.2 Primary Analysis of Primary Endpoint(s)/Outcome(s)

Aim: The change in *S. aureus* abundance after 7 days of AMT cream by using skin swabs to determine the quantity of *S. aureus* using culture and qPCR.

For each AD subject, the abundance of *S. aureus* will be calculated using CFU counts from baseline (day 28) to Day 35 after 7 days of AMT cream application or placebo application. Comparisons of *S. aureus* reduction will be made between AMT cream and placebo subjects using a two-tailed t-test for independent samples with type II error rate of 0.2 and type I error rate of 0.05. The sample size will include 18 subjects in the AMT cream arm and 9 subjects in the placebo arm. Comparisons of AMT cream versus placebo cream will be reported as means, standard deviations, medians, and minimum and maximum. An intention-to-treat analysis will be conducted that includes all subjects who had at least one follow-up visit after intervention. A per-protocol analysis will also be conducted that includes all subjects who were compliant with the full intervention regimen with no major protocol violations.

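### The primary endpoint is S. aureus by culture and qPCR, but only culture is compared between arms, on a swab taken about 4 hours after live anti-S. aureus bacteria were applied

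*Combined protocol and SAP*

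**What the plan says.** **Endpoint.** Section 13.2.1 has skin swabs used "to determine the quantity of *S. aureus* using culture and qPCR". The synopsis and the aim line of Section 13.4.2 say the same.

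**Analysis.** Under Section 13.4.2, S. aureus abundance "will be calculated using CFU counts from baseline (day 28) to Day 35 after 7 days of AMT cream application or placebo application", and the arms are compared by an independent-samples t-test. (Day 28 and Day 35 there correspond to Day 0 and Day 7 of the schedule.) Section 13.7 also works in colony counts. Section 9.1.4 converts S. aureus qPCR to rCFU/cm², but no part of Section 13.4 compares that quantity between arms.

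**Timing.** Section 8.3: "Subjects will be asked to return to the clinic for Visit 5 approximately 4 hours after last cream application". Also: "Subjects will be asked to refrain from bathing, exercising, or showering starting at 12:01am of Visit 5". Subjects keep soap off the arms until the last clinic visit.

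**Samples.** At Visit 5, "one culture swab and one to two DNA swabs will be taken from the eczematous skin from each arm".

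**Culture method.** Section 9.1.3 suspends the swab in broth with glycerol, freezes it at -80°C and plates it on mannitol salt agar with egg yolk; "coagulase positive and negative *Staphylococcus* will be quantified by manual counting of limiting dilutions of the stock solution".

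**Product.** Section 5.1 says the cream holds only bacteria known to inhibit S. aureus. Section 3.1 gives a target of 1×10^5 CFU per 10 mg per cm² at application. Vehicle is the lotion alone.

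**The concern.** The trial asks whether S. aureus falls on the skin. Four hours after the last application, a swab from the AMT arm may bring over live CoNS chosen because they suppress S. aureus. Both organisms are then grown and counted on the same plates. If the added CoNS inhibit S. aureus on the agar, or hide its colonies, the AMT count falls for a reason unrelated to the skin, and the t-test on CFU cannot tell the two apart.

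qPCR does not depend on growth on a plate, so it is the natural companion measure. The plan names it in the primary endpoint and collects the swabs for it, then specifies no analysis of it.

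A later S. aureus comparison, with less product left on the skin, would also help. Secondary endpoint 3 (lesional) and endpoint 4 (non-lesional) promise one, but their analysis items do not deliver it.

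**Working it through.** **1. The plan's own figure.** Inputs from Section 13.7: means 192.86 and 19.186 CFU/cm², SDs 191.86 and 21.42, two-sided 0.05, power 0.80, 2:1 allocation.
- Pooled SD = √((191.86² + 21.42²)/2) = 136.51.
- Effect size = (192.86 − 19.186)/136.51 = 1.272.
- With 8 placebo and 16 AMT, the noncentral t gives power 0.802. The stated n=24 reproduces, and it rests entirely on CFU.

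**2. Relative load on the skin.** Baseline S. aureus is 192.86 CFU/cm² (Section 13.7).
- At the Section 3.1 target: 1×10^5/192.86 ≈ 519:1.
- At the 3×10^7 CFU/g in Section 6.1.1.1, assuming 10 mg/cm²: 3×10^5/192.86 ≈ 1,556:1.
- Over the release range of 1×10^5 to 1×10^8 CFU/g, same assumption: about 5:1 to 5,185:1.

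**3. What limiting dilution does.** Assume a plate is countable up to 300 colonies and ignore resident CoNS. Expected S. aureus colonies = 300 × 192.86/(192.86 + CoNS recovered). At 1×10^5 CFU/cm² applied:

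| CoNS recovered at 4 h (assumed) | Expected S. aureus colonies | Chance of none |
|---|---|---|
| 100% | 0.58 | 0.56 |
| 10% | 5.7 | 0.003 |
| 1% | 48.5 | about 0 |

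This is noise, not bias. CFU is the count multiplied by the dilution factor, so its expectation stays at 192.86. In the first row the Poisson SD from plating alone is about 192.86/√0.577 ≈ 254 CFU/cm², which costs power. In the last row crowding has largely gone.

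**4. What would bias the comparison.** Only inhibition or masking on the plate moves the mean. Let AMT plates lose a fraction f of S. aureus colonies, with no true effect on skin. The spurious difference is f × 192.86. With 9 v 18, df = 25 and noncentrality = (f × 192.86/SD) × √(9×18/27). Using the Section 13.7 SDs as a common SD for the change:

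| f (assumed) | Chance of p<0.05, SD 136.5 | SD 191.86 |
|---|---|---|
| 25% | 0.13 | 0.09 |
| 50% | 0.38 | 0.22 |
| 75% | 0.70 | 0.43 |
| 90% | 0.85 | 0.57 |

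A 90% loss equals the planned 1-log10 effect by definition. No value of f appears in the documents.

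**5. What the pilot covers.** Section 1.4 reports that "the majority of transplanted CoNS died within 24 hours" and that CoNS at 24 hours were similar to baseline. The sample-size inputs are also 24-hour readings. Neither describes plates at 4 hours.

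**6. Whether another analysis fills the gap.** Secondary endpoint 3 (lesional) and endpoint 4 (non-lesional) in Section 13.2.2 name S. aureus at 1, 2 and 4 days after stopping. The matching items in Section 13.4.4 (3a lesional, 4a non-lesional) list baseline, 1 hour, 4 hours, and 4 and 7 days of cream. Visits 4 and 5 are each set about 4 hours after the last cream, so every listed post-baseline point has a nominal time within about 4 hours of an application. By contrast, lesional item 2a does follow CoNS after stopping, so the samples exist.

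**The case against.** The strongest reply is that the plate mechanism is a hypothesis. The documents contain no plate-interference data and no 4-hour survival figure. The 519:1 ratio and the 56% chance of a zero plate describe dilution, which leaves the mean unbiased. Freezing in glycerol limits growth in the broth, and limiting dilution separates colonies. Every subject must carry antimicrobial CoNS (Section 4.2, criterion 6), so vehicle plates are not free of them. In the pilot, S. aureus fell at 24 hours while CoNS were near baseline, which carry-over does not readily explain. All of this stands, and it limits what can be claimed about size.

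It does not touch the mismatch between endpoint and analysis, or the wrong time points in the two S. aureus items. Nor does it remove the difference between arms: only AMT subjects have live CoNS added, and this trial reads the primary endpoint at 4 hours, not 24.

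Two stronger readings are tempting. A reader might infer that a fall in AMT counts would be produced on the agar. The documents do not support that: the loss fraction is unknown, and at 1% CoNS recovery crowding largely disappears. A reader might also infer that success should require qPCR to agree with culture. That rule would discriminate poorly. With no true effect, qPCR would point the same way about half the time, and because it also counts DNA from dead cells it could miss real killing.

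**Conclusion.** The concern holds as a gap in the analysis plan that should be fixed. The primary endpoint names two assays, one is analysed, and the unused one does not depend on growth on the shared plates. Differential inhibition or masking in the AMT arm is plausible from the product's defining property and the swab timing, but its size cannot be derived from the documents. The 9% to 85% chances of spurious significance rest on assumed losses of 25% to 90%, a common SD taken from Section 13.7 and no true effect on skin. They show sensitivity and do not estimate bias. The absence of any specified S. aureus comparison after stopping is plain from the text and needs no assumption.

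**What to change.** 1. In Section 13.4.2, add the between-arm comparison of change in S. aureus qPCR (rCFU/cm²) from Day 0 to Visit 5, using the DNA swabs already taken, and report it beside the CFU result. State that discordance will be discussed as possible plate carry-over, and that qPCR also counts DNA from dead cells. Do not make the primary conclusion conditional on its direction.
2. In Section 13.4.4, correct lesional item 3a and non-lesional item 4a to the visits 1, 2 and 4 days after stopping (Visits 6 to 8). Record and use actual time since the last cream, because the visit windows are ±7 days.
3. Name the Visit 6 CFU comparison as a supportive carry-over check. Section 3.1 asks all subjects to attend that visit but makes later attendance depend on whether the site has returned to baseline. Note that a null result at Visit 6 may also reflect genuine reappearance of S. aureus, and that the pilot's return of CoNS to baseline followed a single application.

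The cost is SAP wording and a few more comparisons on swabs already scheduled. The downside is that qPCR may understate killing, so the two assays may disagree even when the product works.

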8.4. Unscheduled Visits

If disease activity increases or other concerns arise between regularly scheduled visits, participants should be instructed to contact study personnel and may be asked to return to the study site for an “unscheduled” visit.

8.5. Visit Windows

Study visits should take place within the time limits specified below: the designated visit windows (*i.e.* +/- *n* days) for each scheduled visit are also indicated on the Table of Events

Table 1: Schedule of Events 2:1 randomization of AMT to placebo cream for 1 week of BID application

Study Procedures Visit (V)	V1	V2 (Phone 1) ^{a,b}	Repeat Culture Visit ^c	Repeat Phone Call ^d	V3 (Treatment)	Optional visit 1*	Optional visit 2*	V4 (Resupply)	V5 (End of Treatment)	V6	V7	V8	V9 (phone 2)
Day (D), visit window (d= day, h= hours)	D -60 to -2	D -59 to -1	D -31 to -2	D -30 to -1	D0	D0, 1 h after V4 +/- 2 h	D0, 4 h after V4 +/- 2 h	D 4 +/- 5d	D7 +/- 7d	D8 +/- 7d	D9 +/- 7d	D11 +/- 7d	D38 +/- 7d
Screening/Baseline:													
Informed consent	X												
Inclusion/ Exclusion	X	X	X	X	X								
Medical history/ demographics	X		X		X								
Physical exam	X		X		X								
Con meds/procedures	X		X		X			X	X	X	X	X	
Screening skin culture swabs	X		X										
Treatment:					X								
Apply AMT cream or vehicle cream					X								
Dispense IP						X		X					
Dispense Subject Diary						X		X					
Returned unused creams								X	X				
Collect Subject Diary								X	X				
Efficacy:													
Skin swabs						X	X	X	X	X	X	X	
SCORAD	X					X		X	X	X	X	X	
EASI	X					X		X	X	X	X	X	
Photos	X		X		X			X	X	X	X	X	
Safety:													
Weight	X												
Height	X												
Vital Signs	X		X		X			X	X	X	X	X	
Skin exam	X		X		X	X	X	X	X	X	X	X	
Adverse events	X	X	X	X	X	X	X	X	X	X	X	X	
Testing													
Pregnancy test (urine)	X		X										

- Screened subjects who are + for *Staph aureus* and *CoNS* will be contacted via telephone to schedule their treatment initiation Day 0 visit.
- Subjects who are negative for *Staph aureus* and/or *CoNS* and agree to medication washout will be contacted via telephone to schedule a repeat culture visit.
- Only subjects who are negative for *Staph aureus* and/or *CoNS* and agree to washout will return for a repeat culture visit.
- Only subjects who complete the repeat culture visit will have a repeat phone call.
- Only subjects who agree to participate in optional visits, as indicated on their informed consent form, will complete this visit.

9.1 Skin swabs Samples

9.1.1. Skin Swab collection

The antecubital fossae bilaterally will be defined as the lesional swab location. The non-lesional swab location will be defined as the upper inner arm without AD skin. The designated site for swabbing will be marked with a pen and non-identifying digital photographs will be taken of the swabbing site for future visits. The designated site for swabbing will be measured for each subject, and the total area (cm x cm) recorded. Using a skin swab, the lateral edge of the swab will be rubbed across the measured area in a cross-wise manner while rotating the swab handle between the thumb and forefinger. Swabbing will be performed for at least 30 seconds. Up to 6 swabs may be obtained from each site.

9.1.2. *Staphylococcus aureus* Screening assay

Skin swabs will be collected from pre-measured areas of lesional and non-lesional skin per Section 9.1.1. Swabs will be resuspended in 1.5 mL tryptic soy broth (TSB) containing 15% (v/v) glycerol. Dilutions of culture medium will then be used to inoculate on mannitol salt agar plates with egg yolk for selective growth of *Staphylococcus* species and differentiation of coagulase-positive and coagulase-negative strains. Plates will be incubated for 24 hours in a 5% CO₂ incubator at 37° C. The plates will be evaluated for the presence of *S. aureus* colonies, which appear yellow with a surrounding clear zone.

9.1.3. 9.1.2. CFU Quantification of Live *Staphylococcus aureus*

Skin swabs will be collected from pre-measured areas of lesional and non-lesional skin per Section 9.1.1. Swabs will be suspended in 1.5 mL tryptic soy broth (TSB) containing 15% (v/v) glycerol and stored frozen at -80°C. Live CFUs of coagulase positive *S. aureus* will be determined by inoculation on a bacterial culture plate containing mannitol salt agar with egg yolk for selective growth of *Staphylococcus* spp. *S. aureus* will be conventionally distinguished from coagulase negative *Staphylococcus* according to mannitol metabolism and the egg yolk reaction, and coagulase positive and negative *Staphylococcus* will be quantified by manual counting of limiting dilutions of the stock solution.

9.1.4. Quantification of *Staphylococcus aureus*, *S. hominis*, *S. epidermidis*, and total *Staphylococcus* DNA by q PCR

To collect bacterial DNA, pre-measured areas similar to those used for bacterial culture will be rubbed with a swab pre-moistened with Tris-EDTA buffer containing 0.1% TritonX-100 and 0.05% Tween-20 (w/v). Bacterial-genomic DNA will be extracted for quantitative PCR with the UltraClean Microbial DNA Isolation Kit (Mo Bio Laboratories:12224). DNA will be eluted with 50uL DNase free water. 0.5 µL of the elution will be used for quantitative real-time PCR (qPCR) using universal 16SrRNA primers and species-specific primers. For quantification of *S. aureus*, *S. epidermidis* and *S. hominis* DNA, DNA extracted from an authentic number of each bacteria (ATCC35556, ATCC12228 and ATCC27845, respectively) will be used for standard curve. The standard curve will be used for determination of absolute number of bacteria (CFU/uL). This known amount of bacteria for *S. aureus* and *CoNS* will range from 1x 10¹ to 1x10⁶ CFU/microliter. The absolute number of bacteria will then be converted to relative CFU (rCFU)/cm² based on pre-measured swab area.

We have confirmed that each primer set does not cross-react to other species of bacteria. In addition, we have confirmed specificity of primer sequence by BLAST search.

For total 16SrRNA quantification, relative abundance will be calculated with the $\Delta\Delta Ct$ method. The following universal 16S primer set will be used to determine relative abundance of 16S rRNA gene according to the reference [J Clin Microbiol 43, 5332-5337 (2005)]. This universal primer set covers 79% of Proteobacteria, 85% of Actinobacteria, 72% of Firmicutes, and 61% of Bacteroidetes. Thus, the reactivity of this primer set differs depending on bacteria genus level. Therefore, we cannot determine absolute abundance of 16S rRNA gene from bacterial mixture using a standard curve of bacterial DNA extracted from single species. Accordingly, we will determine relative abundance of the total 16S rRNA gene. We will determine relative abundance of 16S rRNA gene by comparing it to baseline abundance. Baseline will be set to 1 and relative abundance will be determined by the Delta-Delta-Ct method.

10. Biospecimen Storage

Instructions for sample preparation, handling, storage, and shipping are included in the MOOP. The Principal Investigator (PI) will be responsible for acknowledging and implementing all the regulations for classification, sample handling, packaging and labeling, permits or authorizations, and personnel training for shipment of biological and hazardous materials required for the conduct of this study.

Isolated and speciated *CoNS* strains that have been chosen for use in the AMT cream will be stored at -80 degrees C in 15% TSB-glycerol medium until ready to be used for formulating each subject's AMT cream.

Each subject will be assigned a unique numerical identifier. All bacterial stocks will be stored at -80 degrees C in Eppendorf tubes. Each tube will be labeled with subject's unique numerical identifier as well as a separate bacteria identifier linked to the bacteria stock in the tube. The key explaining the contents of each of the bacteria identifiers to what they are will be stored in the laboratory notebook for the AMT study.

Any bacteria stock that is unused after the completion of this protocol will be disposed of as per UCSD's hazardous waste protocol.

11. Criteria for Participant and Study Completion and Premature Study Termination

